6.1.3. Data Derivation for weekly average of PI-NRS

The weekly average of an efficacy variable in an analysis week will be calculated as follow:

$$\frac{\sum \text{non-missing efficacy variable in an analysis week}}{\text{Number of days with non-missing efficacy variable in the analysis week}} \quad [1]$$

Where the efficacy variable will be

- Daily average PI-NRS pain score over the past 24 hours
- Daily worst PI-NRS pain scores over the past 24 hours

If all of the data are missing within an analysis week, the average of the efficacy variable within the analysis week will be missing.

6.2. Primary Efficacy Endpoint and Analysis

6.2.1. Definition

The primary efficacy endpoint is the change from baseline to week 12 in the weekly average of the daily average PI-NRS score over the past 24 hours.

Baseline is defined as the last 14 days before the first dose of IMP (Visit 3). The analysis weeks for post-baseline will be derived using rule described in [Table 2](#).

The baseline and post baseline weekly average of the daily average PI-NRS pain scores over the past 24 hours will be derived using formula [1], respectively.

6.2.2. Primary Efficacy Analysis

The primary efficacy endpoint will be analyzed using a MMRM model with change from baseline in the average of the daily average PI-NRS score over the past 24 hours at weeks 1, 2, 3, 4, 5, 6, 7, 8, 9, 10, 11, and 12 as the dependent variable, sex, age group at FM onset, week, treatment, and treatment by week interaction as fixed factors, and baseline average of the daily average PI-NRS score as a covariate. The heterogeneous autoregressive correlation structure [ARH (1)] for repeated observations within patients will be used, and the denominator degrees of freedom will be estimated using Kenward-Roger’s approximation. An adjustment for missing data due to lack of efficacy or adverse events assumes the PI-NRS scores will be on average return to baseline values. Missing data (due to early treatment discontinuation or missing e-dairy recording in an entire analysis week) will be imputed 500 times to generate 500 complete data sets using the SAS procedure PROC MI following the 3 steps below.

Notes, if ARH(1) does not converge, then simpler covariance structures with less parameters will be used in the following order until the model converges: autoregressive (1) (AR[1]); heterogeneous compound symmetry (CSH); and compound symmetry (CS).

Step 1: The monotone missing pattern will be induced by the Markov Chain Monte Carlo method in the PROC MI procedure using seed number 4751523.

The average of the daily average PI-NRS score up to and including week 12 will be imputed by using following SAS code to impute the arbitrary missing data and to make the missing data pattern monotonic:

```
PROC MI DATA=name NIMPUTE= 500 SEED=4751523 OUT= MI_MONOTONE;  
  BY TRT01PN AGEATFMONST SEX;  
  MCMC IMPUTE= MONOTONE;  
  VAR BASE WEEK1 ... WEEK12;  
RUN;
```

Where TRT01PN denotes the planned treatment group; AGEATFMONST denotes the age group at FM onset; BASE denotes the baseline average of the daily average PI-NRS score; WEEK1, . . . , WEEK12 denote the weekly average of the daily average PI-NRS score in weeks. In bold are the SAS key words.

Statistical Analysis Plan

Step 2: Once the arbitrary missing data are imputed, the following SAS code will be used to impute the monotone missing data.

The remaining missing data at subsequent weeks will be imputed using the regression method for the monotone pattern with seed number 4751523 and adjustment for covariates including baseline value and all values at preceding weeks.

```
PROC MI DATA= MI_MONOTONE NIMPUTE= 1 SEED= 4751523
OUT= MI_COMPLETE;
  CLASS TRT01PN AGEATFMONSET SEX;
  MONOTONE REG;
  VAR TRT01PN AGEATFMONSET SEX BASE WEEK1 ... WEEK12;
RUN;
```

MI_COMPLETE will be transposed to a new data set (WEEKPI0) with each week as a row.

Step 3: Use by-week mean change from baseline to adjust those who discontinued treatment due to lack of efficacy (LOE) or adverse event (AE) before week 12.

The initially missing and now imputed data for patients who discontinued from the study drug due to LOE or AE will be center adjusted at the mean baseline value. That is, the final imputed score will be equal to the imputed score under missing at random minus the observed mean change from baseline score at the post baseline time point.

```
DATA WEEKPI;
  SET WEEKPI0;
  CHANGEi = AVALi - BASE;
  IF DTREAS IN ('LACK OF EFFICACY', 'ADVERSE EVENT') AND IMP= 1
  THEN DO;
    CHANGEi = CHANGEi - MWEEK_CHG;
  END;
RUN;
```

Where AVALi denotes the value of the post baseline weekly average of the daily average PI-NRS after missing data imputation; CHANGEi denotes the change from baseline after missing data imputation; MWEEK_CHG denotes the change from baseline calculated without missing data imputation; DTREAS denotes the reason for treatment discontinuation.

Step 4: Each of the 500 imputed data sets described above steps will be analyzed using the MMRM. SAS code is:

```
ODS OUTPUT LSMEANS= LS DIFFS = DIFF (WHERE = (week = _week));
PROC MIXED DATA= WEEKPI (WHERE= (WEEK>= 1));
  BY _IMPUTATION_;
  CLASS SUBJID TRT01PN WEEK AGEATFMONSET SEX;
  MODEL CHANGEi= BASE TRT01PN AGEATFMONSET SEX WEEK
    TRT01PN*WEEK/DDFM=KR;
  REPEATED WEEK/SUBJECT= SUBJID TYPE= ARH(1);
  LSMEANS TRT01PN*WEEK / DIFF CL;
RUN;
ODS OUTPUT CLOSE;
```

Statistical Analysis Plan

Where `_IMPUTATION_` denotes the numbering of imputations; `SUBJID` denotes the subject ID; `WEEK` denotes the analysis week (12 levels: weeks 1 to 12).

Step 5: The results from the 500 analyses from Step 4 will be combined using Rubin’s formulae (`PROC MIANALYZE`). The least square (LS) mean estimates for the mean change from baseline to each time point, as well as the difference of the estimates between the fremanezumab and placebo group, with the corresponding SE, p-value and associated 95% CI will be provided.

(a) For LS means

```
PROC SORT DATA= LS;  
  BY WEEK TRT01PN _IMPUTATION_ ;  
RUN;  
  
ODS OUTPUT PARAMETERESTIMATES= LSM_O;  
PROC MIANALYZE DATA= LS;  
  BY WEEK TRT01PN;  
  MODELEFFECTS ESTIMATE;  
  STDERR STDERR;  
RUN;  
ODS OUTPUT CLOSE;
```

Where `ESTIMATE` and `STDERR` are LS mean and standard error from Step 4.

(b) For treatment difference, treatment difference CI and p-values

```
PROC SORT DATA= DIFF;  
  BY WEEK TRT01PN _TRT01PN _IMPUTATION_ ;  
RUN;  
  
ODS OUTPUT PARAMETERESTIMATES= DIFF_O;  
PROC MIANALYZE DATA= DIFF;  
  BY WEEK TRT01PN _TRT01PN;  
  MODELEFFECTS ESTIMATE;  
  STDERR STDERR;  
RUN;  
ODS OUTPUT CLOSE;
```

The observed data (ie, without imputation for missing data) will be summarized using descriptive statistics by analysis weeks (baseline, weeks 1 to 16).

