9.6.4. Planned Method of Analysis

9.6.4.1. Primary Efficacy Analysis

The primary efficacy variable will be analyzed using an MMRM model with the change from baseline up to week 16 in the weekly average of the daily average over the past 24 hours PI-NRS scores as the dependent variable; sex, age group at FM onset, week, treatment, and treatment by week interaction as fixed factors; and baseline PI-NRS scores as a covariate. The heterogeneous autoregressive correlation structure for repeated observations within patients will be used, and the denominator degrees of freedom will be estimated using Kenward-Roger's approximation. An adjustment for missing data due to lack of efficacy or adverse event assumes the PI-NRS scores will, on average, return to baseline values. Missing data will be imputed 500 times to generate 500 complete data sets by using the SAS procedure PROC MI following the 3 steps below:

- Step 1: The monotone missing pattern will be induced by the Markov Chain Monte Carlo method in the PROC MI procedure using seed number 4751523.
- Step 2: The remaining missing data at subsequent weeks will be imputed using the regression method for the monotone pattern with seed number 4751523 and adjustment for covariates including treatment groups, randomization strata, relevant baseline and all values at preceding visits.
- Step 3: The initially missing and now imputed data for patients discontinued from the study treatment due to lack of efficacy or adverse event will be center adjusted at the mean baseline value for that treatment group, ie, the final imputed score will be equal to the imputed score under missing at random minus (mean change from baseline score at the post-baseline time point for the treatment group).

Each imputed data set will be analyzed using the MMRM described above. The results from the 500 analyses will be combined using Rubin's formulae (PROC MIANALYZE). The least squares means estimates for the mean change from baseline to each time point, as well as the difference of the estimates between the fremanezumab and placebo groups, with the corresponding standard error, p-value and associated 95% confidence interval will be provided.

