
Visit 8 (EOS) was removed. Accordingly, the following assessments were added at Visit 7 (EOT/EOS or ET):
 
 • Blood sample for serum ADA concentration • [REDACTED] 	Visit 7 (EOT/EOS or ET)	Removed Visit 8 to shorten the duration of patient participation and reduce patient burden. Given this removal, added more assessments (eg, ADA blood sample collection) to Visit 7 to serve the purpose of Visit 8.
Day and allowed time window for Days 29, 57, 85, and 113 ±3 7 days	Day and allowed time window for Days 29, 57, 85, and 113 ±7 days	To provide flexibility and reduce patient burden

Original text with changes shown	New wording	Reason/justification for change

At Visits 4 and 5, the following assessments were removed:
 
 • Clinical laboratory tests (serum chemistry, hematology, and urinalysis) • Blood samples for plasma concentration of IMP • Blood sample for serum ADA concentration • XXXXXXXXXX 		To reduce patient burden

At Visits 4 and 6, the following procedure was added: Inform patients of study restrictions and compliance
		To improve patient compliance

Alcohol screen (social history)^m
	Alcohol (social history) ^m	Clarification

The injection site reactions assessment was deleted
		Injections site reactions will be spontaneously reported and included in adverse event assessment

A footnote c was added to Visits 4 and 5. c For Visits 4 and 5 (when at-home dosing is available), home visits are permitted for patients who are not able to go to the investigational center or if the investigational center staff are not able to see patients at the investigational center (see Section 3.5).
	
c For Visits 4 and 5 (when at-home dosing is available), home visits are permitted for patients who are not able to go to the investigational center or if the investigational center staff are not able to see patients at the investigational center (see Section 3.5).
	Clarified that visits can also occur at home

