6.1.2. Baseline and Analysis Weeks for Data Collected Daily

Baseline is defined as the last 14 days before the first dose of IMP (day -14 to day -1). Day 1 will be defined as the day of first dose of IMP (Visit 3).

For data collected daily (eg. PI-NRS scores), analysis weeks will be derived using algorithm in Table 2. Analyses will be based on the derived analysis weeks.

Table 2: Analysis Weeks

4-Week Interval	Visit	Dose (n)	Target Injection or Visit Day	Actual Injection or Visit Day	Analysis Week	Analysis Week Interval
1 ^a	3	1	1	1	1	[1, v-22]
					2	[v-21, v-15]
					3	[v-14, v-8]
					4	[v-7, v-1]
2 ^a	4	2	29	v (2 nd dosing day)	5	[v, x-22]
					6	[x-21, x-15]
					7	[x-14, x-8]
					8	[x-7, x-1]
3 ^a	5	3	57	x (3 rd dosing day)	9	[x, y-22]
					10	[y-21, y-15]
					11	[y-14, y-8]
					12	[y-7, y-1]
4 ^b (last dose)	6	4	85	y (4 th dosing day)	13	[y, y+6]
					14	[y+7, y+13]
					15	[y+14, y+20]
					16	[y+21, y+27]
5	5	EOT	113		-	-

^a In 4-week intervals before the last dose, the 4th week will be 7 days before the date of the injection, and counting backward by 7-day increments to define remaining weeks. The 1st week of these 4-week intervals will include all remaining days in the interval.

^b The weeks after the last dose, an analysis week will be defined as a 7-day interval counting onward.

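### Step 1 of the primary imputation fits 13 variables separately in 12 cells, some of which may be too small to support the fit, and the SAP gives no rule for a short cell

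*SAP*

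**What the plan says.** SAP 6.2.2 imputes in stages. Step 1 makes the missing-data pattern monotone by MCMC on the baseline average and the 12 weekly averages, under "BY TRT01PN AGEATFMONST SEX". Step 2 then imputes what remains by regression. It has no split by cell; treatment and both strata are entered as variables: "VAR TRT01PN AGEATFMONSET SEX BASE WEEK1 ... WEEK12".

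The only contingency in the section is "if ARH(1) does not converge, then simpler covariance structures with less parameters will be used". The list that follows (AR(1), CSH, CS) concerns the MMRM covariance, not the imputation model. The Step 1 code names no prior, minimum cell size or pooling rule.

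Protocol 9.6.4.1 describes Step 1 without any split. Its strata enter at Step 2, through "adjustment for covariates including treatment groups, randomization strata, relevant baseline and all values at preceding visits".

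Two rules decide when Step 1 has anything to fill. SAP 6.1.3 states: "If all of the data are missing within an analysis week, the average of the efficacy variable within the analysis week will be missing". SAP 6.1.2, Table 2, counts weeks backward from the next dose, and its footnote adds: "The 1st week of these 4-week intervals will include all remaining days in the interval". That first week can therefore shrink or vanish when two doses are close together.

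Step 5 reports more than week 12: "The least square (LS) mean estimates for the mean change from baseline to each time point".

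**The concern.** Three arms, two onset-age groups and two sexes give 12 cells, each needing its own 13 means and 91 variances and covariances. Randomization is stratified by sex and onset age, but nothing fixes how many patients fall in each stratum, so some cells may be small. In a short cell the stated rule cannot be estimated from that cell's data, and the SAP does not say what happens next. A primary-analysis step would then depend on software defaults or on a choice made during the analysis.

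The same imputation is reused for the rescue-medication sensitivity analysis (SAP 6.2.3), the 30% and 50% responder analyses (6.3.3) and the worst-pain endpoint (6.3.4).

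**Working it through.** **Inputs.** Step 1 grouping and variables: SAP 6.2.2. Strata: SAP 2.2. Planned 240 patients, 80 per arm, SD 2.2: SAP 2.4. Enrolment of 153: Protocol amendment history, Amendment 05. Early stop for futility: SAP 2.5. Not given: final N, sex mix, onset-age mix, visit scatter, diary completion.

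**The plan's own figure.** The planned size rests on a precision statement, not on cell sizes. With 80 per arm, the half length is t(0.975, 158) × s × √(2/80). With true SD 2.2, the probability that it is below 0.74 is 0.918, so the stated figure of at least 90% reproduces. It says nothing about Step 1.

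**Rank.** Cells: 3 × 2 × 2 = 12. Variables: 1 + 12 = 13. The sample covariance from n patients has rank at most n − 1. A numerical check gives rank 12 at n = 13 (singular) and 13 at n = 14. Fourteen is necessary, not sufficient: if one of 14 patients has a gap, 13 complete patients remain to estimate 13 coefficients (intercept plus 12), leaving no residual degrees of freedom.

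**How many patients that needs.** 12 × 14 = 168, evenly spread. At N = 153 the average cell is 153/12 = 12.75, so at least one cell is short whatever the mix. At N = 240 the average is 20 and the answer depends on the mix (assumed, and taken as equal across arms):

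| Onset-age split | Smaller age stratum per arm | Share the smaller sex needs there |
|---|---|---|
| 50/50 | 40 | 14/40 = 35% |
| 60/40 | 32 | 14/32 = 44% |
| 65/35 | 28 | 14/28 = 50% |

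With an age split more uneven than 65/35, at least one cell is short for any sex mix.

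**When a gap exists.** A fully missed diary week is one source. Table 2 is another, with dose 2 on day v, dose 3 on day x and dose 4 on day y:
- Week 1 is [1, v−22], empty if v = 22, the edge of the ±7-day window.
- Week 5 is [v, x−22] and week 9 is [x, y−22], each empty if consecutive doses are 21 or fewer days apart. Within ±7 days the shortest interval is 50 − 36 = 14 days.
- Within ±3 days the shortest interval is 54 − 32 = 22 days, so week 5 or 9 keeps at least one day, and week 1 keeps at least 26 − 22 = 4.

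The change log in Protocol 16.3 shows the window widening from ±3 to ±7 days: "Day and allowed time window for Days 29, 57, 85, and 113 ±3 7 days". Before that, visits 4 to 7 days off were allowed as deviations, and only through these could timing alone empty a week.

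The frequency of timing gaps is not in the documents. By simulation with rounded normal visit scatter (SD 2, 3, 4 days, assumed) and no missed entries, within ±7 days:
- each visit timed 28 days from the previous dose: about 0.1%, 2.0–2.5% and 6.5–8.0% of patients have an empty week 1, 5 or 9;
- visits scattered independently around their target days: 2.2%, 11.9% and 20.7%.

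**Noise in estimable cells.** For predicting one week from k other variables with n complete patients, the prediction variance relative to the residual variance is (1 + 1/n)(n − 2)/(n − k − 2).
- Cell level, k = 12: n = 16 gives 1.0625 × 14/2 = 7.44; n = 20 gives 1.05 × 18/6 = 3.15.
- Arm level with sex and onset age added, k = 14: n = 56 gives 1.37; n = 80 gives 1.23.

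**The case against.** The strongest reply is that this hardly touches the primary result. The endpoint is week 12, and dropout and missing week-12 values are imputed in Step 2, which pools all cells. Gaps should be uncommon: a single entry keeps a week non-missing, a make-up report is offered the next day (SAP 6.1.1), and diary data are reviewed centrally every day (Protocol 3.5). All of this stands.

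The noise ratio also looks worse than its effect on a reported mean. As a rough gauge, assume 8%/3 = 2.7% of patients have a gap at a given week, residual variance is 10–30% of the total, and every gap lies in a 16-patient cell. The variance of the arm mean then rises by 0.027 × 0.10 to 0.30 × (7.44 − 1.23), or 1.7–5.0%, and its SE by about 0.8–2.5%. That gauge covers estimable cells only, not short ones.

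A reader might multiply the gap rate by the dropout rate to get the share of week-12 values that depend on Step 1. Table 2 does not support that. A timing gap in week 9 requires dose 4, which comes after week 12. A timing gap in week 5 requires dose 3, so only dropout between doses 3 and 4 could combine with it.

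A reader might also call the cell split a breach of the protocol. Protocol Section 9 leaves further detail to the SAP, and the SAP introduction says the SAP prevails, so imputing by stratum is allowed. The contrast shows only that the protocol does not require the split.

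**Conclusion.** The point holds as a minor specification error. Step 1 may not be estimable in some cells, and no rule covers that case. The filled values are affected only in a short cell that also has an intermittent gap. The effect falls mainly on the earlier-week estimates and is indirect for week 12. In cells that can be fitted, the split still makes filled values much noisier than an arm-level fit would.

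Two stronger readings are not supported. First, a reader might infer from the 153 enrolled that short cells are certain. That is a count at Amendment 05, not the final N; certainty requires an analysed N below 168, and above that it depends on an unreported mix. Second, a reader might infer that patients would drop out of the mITT analysis. That depends on how the software treats a singular cell, which the documents do not state.

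The rank result and cell count need no assumption. The gap rates, stratum splits and SE gauge rest on the assumed ranges shown.

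**What to change.** By SAP amendment before database lock, which SAP 2.5.2 provides for:
- In Step 1, replace the grouping by `BY TRT01PN;` and put sex and onset-age group, as fully observed 0/1 variables, first in the VAR list. With 15 variables the complete-data minimum is 16 patients per arm, 3 × 16 = 48 in total instead of 168. At N = 153 the arms average 51.
- Use one spelling of the onset-age variable; it is AGEATFMONST in Step 1 and AGEATFMONSET in Step 2.
- Apply the same code to the rescue-medication sensitivity, responder and worst-pain analyses.

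The cost is a small code change and a sentence of text. No protocol change is needed, because the protocol's Step 1 specifies no split. The downside is a common covariance across sex and onset-age strata within an arm, which Step 2 already assumes.

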For analysis purpose, a dichotomous scale of 'Yes' or 'No' will be derived. Scale "much improved" or "very much improved" will be considered improved (Yes), and all other non-missing responses will be considered not improved (No). Missing category will be presented as appropriate.

The response variable (yes or no) at week 12 will be analyzed using a logistic regression model with the treatment, age group at FM onset, and sex as explanatory factors. Missing category will not be included.

SAS code is:

```
ods output diffs = dif LSMeans = ls;  
PROC GENMOD DATA =name;  
CLASS TRT01PN STRATAR SEX;  
MODEL AVALCAT1 = TRT01PN STRATAR SEX / DIST=BIN TYPE3;  
LSMEANS trt01pn/exp DIFF CL;  
RUN;  
ods output close;
```

Statistical Analysis Plan

```
data ls;
set ls;
** p = estimated response rate;
p = logistic(estimate);
p_l = logistic(Lower);
p_u = logistic(Upper);
run;
```

Where AVALCAT1 denotes the responses with ‘yes’ for improved and ‘no’ for not improved.

In addition, the PGIC data will be summarized as a categorical variable using descriptive statistics for all visits, including missing category as appropriate.

6.3.3. Percentage of Patients Who Experience a $\geq 30\%$ or $\geq 50\%$ Reduction in the Weekly Average of the Daily Average PI-NRS Score at Week 12

The weekly average of the daily average PI-NRS score with missing data imputation from the 500 imputed data sets derived as described in steps 1 to 3 of Section 6.2.2 will be used to calculate the pain intensity reduction (%) from baseline in the weekly average of the daily average PI-NRS score using formula [2].

$$\frac{\text{baseline value} - \text{postbaseline value}}{\text{baseline value}} \times 100\% \quad [2]$$

The percentage of patients who experience $\geq 30\%$ reduction and $\geq 50\%$ reduction in the weekly average of the daily average PI-NRS score at week 12 will be analyzed using a generalized estimating equation (GEE) method where the dependent variable is $\geq 30\%$ reduction (Yes/No) or $\geq 50\%$ reduction (Yes/No), respectively, [REDACTED]

SAS code for GEE model:

```
ods output LSMeans = ls;
PROC GENMOD DATA =name;
  BY _IMPUTATION_;
  CLASS SUBJID TRT01PN WEEK STRATAR SEX;
  MODEL AVALCAT = BASE TRT01PN WEEK STRATAR SEX
          TRT01PN*WEEK/ DIST=BIN TYPE3;
  REPEATED SUBJECT = SUBJID / TYPE = AR(1);
  LSMEANS trt01pn*week/exp DIFF CL;
RUN;
ods output close;
```

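### The Step 2 imputation code in SAP 6.2.2 has no `BY _IMPUTATION_`, so as printed it does not produce the 500 separate imputations the primary analysis needs

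*SAP*

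**What the plan says.** SAP 6.2.2 states the intention plainly. Missing weekly scores are to be imputed 500 times. Step 4 reads "Each of the 500 imputed data sets described above steps will be analyzed using the MMRM", and its code runs by imputation number. Step 5 begins "The results from the 500 analyses from Step 4 will be combined using" and applies Rubin's formulae. Protocol 9.6.4.1 describes the same procedure.

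The code is presented as the code to be used. Step 1 runs PROC MI with 500 imputations and writes `MI_MONOTONE`. Step 2 then runs "PROC MI DATA= MI_MONOTONE NIMPUTE= 1 SEED= 4751523" with CLASS, MONOTONE and VAR statements. It has no BY statement, and the imputation number is not among its variables. The only processing described before Step 3 is "MI_COMPLETE will be transposed to a new data set (WEEKPI0) with each week as a row".

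The variable names also disagree. Step 1 has "BY TRT01PN AGEATFMONST SEX", while Step 2 has "CLASS TRT01PN AGEATFMONSET SEX" and Step 4 uses the Step 2 spelling. The responder code in SAP 6.3.3, which reuses these imputed sets, has "CLASS SUBJID TRT01PN WEEK STRATAR SEX".

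**The concern.** Multiple imputation gives an honest standard error because each completed data set is built from its own draw of the imputation-model parameters. Fitting Step 2 to the whole stack removes that: there is one fit per week and one parameter draw for all 500 copies. The listing then does not deliver the analysis the text describes.

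The standard error matters here. The primary objective is to estimate the treatment effect, and SAP 2.4 justifies the sample size by the half-length of the confidence interval. The same imputation steps feed the rescue-medication sensitivity analysis (6.2.3), the 30% and 50% responder analyses (6.3.3) and the worst-pain analysis (6.3.4). Because the text makes the intention clear, the risk is confined to the listing being copied into the production program.

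**Working it through.** **The plan's own precision figure.** With SD 2.2 and 80 per arm, the half-length is t(0.975, 158) × S × √(2/80).
- At S = 2.2: 1.975 × 2.2 × 0.1581 = 0.687.
- The half-length is below 0.74 when S < 0.74 / (1.975 × 0.1581) = 2.370, that is, when a chi-square on 158 df is below 158 × (2.370/2.2)² ≈ 183.3.
- That probability is 91.8% at 80 per arm (89.7% at 79), so the stated figure of at least 90% reproduces. It allows nothing for dropout.

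**Reading the code.** Steps 1, 4 and 5 and the responder code all carry a BY statement; Step 2 does not. Two outcomes are possible, and the documents cannot settle which applies.
- *Index survives.* Each weekly regression is fitted to about 500 × N rows. Its coefficients are drawn once, with posterior variance about 1/500 of the proper value, and shared by all copies.
- *Index reset by* `NIMPUTE= 1`. Step 4 has one BY group with 500 records per patient-week, and Step 5 has one set to pool.

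Because of the onset-age spelling, the blocks do not run together as printed, so either outcome needs that repaired first.

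**Why the standard error falls if the index survives.** Rubin's total variance is T = W + (1 + 1/M)B. Parameter uncertainty should enter B, but with one shared draw it drops out.

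**Simulation inputs.**
- From the documents: three arms, 80 per arm, 12 weekly values, SD 2.2 at week 12, and the Step 3 shift using the observed mean ("MWEEK_CHG denotes the change from baseline calculated without missing data imputation"), taken by arm as in Protocol 9.6.4.1. A smaller case uses 153/3 = 51 per arm, from the count randomised at Amendment 05.
- Assumed: SD 1.2 at week 1 rising linearly, first-order correlation, baseline SD 1.2, mean week-12 change −1.5, 20% male, an even onset-age split, dropout completely at random over weeks 2–12, and no intermittent gaps.
- Week-12 ANCOVA stood in for the MMRM, with 100 imputations and 3,000 paired trials per cell.

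**Standard error without BY, relative to with BY (25% dropout).**

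| Per arm | Correlation | No dropouts shifted | 20% shifted |
|---|---|---|---|
| 80 | 0.7 | 0.937 | 0.938 |
| 80 | 0.9 | 0.957 | 0.958 |
| 80 | 0.95 | 0.972 | 0.972 |
| 51 | 0.9 | 0.942 | 0.943 |

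At 80 per arm, B without BY is 0.633, 0.667 and 0.683 of its proper value at correlation 0.7, 0.9 and 0.95.

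A second simulation, written separately, gave 3–6% below for correlation 0.80–0.95 or a random-intercept pattern, and up to 7% below for 0.5–0.7. At 15% dropout it gave 1.4–2.7%; at 35%, about 5–10%. Its 0.9 case, with half the dropouts shifted, shows where the loss arises:
- With BY: T = 0.3957² = 0.1566; B = 0.190 × 0.1566 = 0.0298; W = 0.1268.
- Without BY: T = 0.3776² = 0.1426; B = 0.136 × 0.1426 = 0.0194; W = 0.1232.
- B falls by 0.0104 and W by 0.0036; the SE ratio is 0.3776/0.3957 = 0.954.

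**Coverage, by share of dropouts leaving for lack of efficacy or adverse events** (80 per arm, 25% dropout, correlation 0.9; Monte Carlo error about 0.4 points or less).

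| Share shifted | 0% | 5% | 10% | 20% | 50% | 100% |
|---|---|---|---|---|---|---|
| True SD of estimate | 0.386 | 0.382 | 0.378 | 0.371 | 0.347 | 0.310 |
| SE without BY | 0.374 | 0.375 | 0.376 | 0.378 | 0.383 | 0.389 |
| SE with BY | 0.391 | 0.392 | 0.393 | 0.395 | 0.399 | 0.405 |
| Coverage without BY (%) | 94.0 | 94.3 | 94.6 | 95.1 | 96.9 | 98.5 |
| Coverage with BY (%) | 95.0 | 95.2 | 95.4 | 96.3 | 97.8 | 98.8 |

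At 20% shifted, mean half-widths are 0.741 without BY and 0.774 with it, a difference of 0.03 points on a 0–10 scale. With a true effect of −0.7 and 50% shifted, the mean estimate is −0.622 either way. The stress case (51 per arm, 40% dropout, no shift) gives a ratio of 0.882 and coverage of 92.5% against 95.7%.

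**The case against.** The plan's intention is not in doubt: the text, Step 4, Step 5 and the protocol all describe 500 separate analyses. The listing is also schematic. It has a placeholder data set name, describes the transpose in words only, and does not show how the Step 3 variables are merged in, so a programmer must edit it before it runs. This stands, and it makes the point an error in the listing and not a wrong method. But none of those edits would by itself reveal the missing BY line.

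The 3–6% figure applies to only one of two outcomes and rests on dropout, correlation and shift share that the documents do not give. That also stands, and the figure should be read only as conditional. The simulation left Step 1 inactive. Intermittent gaps would add some between-copy variation even without BY, and that effect on the ratio was not tested.

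The practical harm is slight in a proof-of-concept trial already stopped for futility. That is fair.

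Finally, `STRATAR` may be defined behind the redaction beside the responder model. It may, but no definition is visible in the SAP. The PGIC code in 6.3.2 uses the same name where the unredacted text says age group at FM onset. This naming matter is editorial and secondary to the missing BY.

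**Conclusion.** The concern holds, and it is minor. That Step 2 omits `BY _IMPUTATION_`, and that nothing printed restores the separation, can be read directly from SAP 6.2.2; in neither outcome does the listing give the specified multiple imputation.

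If the index survives, the week-12 standard error is about 3–6% too small relative to the correct Rubin standard error, under the assumed 25% dropout and 80 per arm. This is a shortfall against the specified analysis and not a demonstration that the interval under-covers. The Step 3 shift reduces the true variability of the estimate while Rubin's formula does not follow, so the as-printed interval stays near or above 95% once roughly 10–20% or more of dropouts leave for lack of efficacy or adverse events. The documents give neither that share nor the dropout rate. If the index is reset, the failure is gross and would be seen.

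**What to change.** Sort `MI_MONOTONE` by `_IMPUTATION_` (Step 1 output is ordered by its own BY groups) and add `BY _IMPUTATION_;` to the Step 2 PROC MI call. Use one onset-age variable name in Steps 1, 2 and 4 and in the PGIC and responder code, or define `STRATAR`. As a check, confirm that `MI_COMPLETE` holds 500 values of `_IMPUTATION_`, with each mITT patient appearing once per value. The correction carries through to SAP 6.2.3, 6.3.3 and 6.3.4.

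The cost is one sort, one line, one name and the run time of 500 sets of regression fits. SAP 2.5.2 provides for amendments to be approved before database lock, so the correction fits that step.
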